13.1.4 Stability and Storage

Lyophilized Drug Product: Lyophilized Carfilzomib for Injection must be kept in the labeled

drug cartons and stored at 2°C - 8°C (36°F - 46°F) in a refrigerator.

If procedures permit, the refrigerator should be continuously monitored and temperature records retained for review.

The refrigerator should also be on a backup generator and alarmed for temperature deviations if available. Lyophilized Carfilzomib for Injection exposed at any time to temperatures exceeding 30°C / 86°F must be discarded

Reconstituted Drug Product: Once a drug vial is reconstituted and inspected, the clear solution can be stored in a refrigerator (recommended) controlled from 2°C - 8°C (36°F - 46°F) or at room temperature from 15°C - 30°C (59°F - 86°F) until use. Once reconstituted, Carfilzomib for Injection must be used on the day of reconstitution or else it must be destroyed. Prior to administration, all reconstituted drug should be equilibrated to room temperature. **DO NOT FREEZE LYOPHILIZED OR RECONSTITUTED DRUG.**

Diluted Drug Product: After dilution with D5W for clinical use, Carfilzomib should be stored under refrigeration.

13.1.5 Administration Procedures

Carfilzomib will be administered by intravenous infusion over 30-minutes through a peripheral or central venous access device via portable (ambulatory) pump. Care should be taken in placing and maintaining the product container at a level physically higher than the pump to avoid advancing air into the administration set tubing.

If the patient has a dedicated line for carfilzomib administration, the line must be flushed with a minimum of 20 mL of normal saline prior to and after drug administration.

13.1.6 Incompatibilities

In an in vitro study using human liver microsomes, carfilzomib showed modest direct and time-dependent inhibitory effect on human cytochrome CYP3A4/5. Given that the clearance of carfilzomib likely occurs extrahepatically via the activity of epoxide hydrolase and peptidase activities, the clinical relevance of these in vitro results is not clear. No clinically significant drug interactions have been noted to date in patients receiving a variety of agents metabolized by CYP3A4. Moreover, no dose adjustments have been required for any concomitant medication in patients receiving carfilzomib. However, caution should be exercised in administration of concomitant medications which are substrates of human CYP3A4.

13.2 LENALIDOMIDE

13.2.1 Source

REVLIMID® (lenalidomide) is provided to investigator by Celgene Inc. under Cooperative Research and Development Agreement (CRADA).

13.2.2 Toxicity

A comprehensive listing of all toxicities (i.e., very common, common, etc.) are listed in the informed consent document. The approved USPI may also be referenced for current information related to this agent. See below information regarding most significant toxicities:

Fetal Risk: Do not use REVLIMID during pregnancy. Lenalidomide, a thalidomide analogue, caused limb abnormalities in a developmental monkey study. Thalidomide is a known human teratogen that causes severe life-threatening human birth defects. If lenalidomide is used during

pregnancy, it may cause birth defects or death to a developing baby. In women of childbearing potential, obtain 2 negative pregnancy tests before starting REVLIMID® treatment. Women of childbearing potential must use 2 forms of contraception or continuously abstain from heterosexual sex during and for 4 weeks after REVLIMID treatment.

Hematologic Toxicity: REVLIMID can cause significant neutropenia and thrombocytopenia.

In the pooled MM studies Grade 3 and 4 hematologic toxicities were more frequent in patients treated with the combination of REVLIMID and dexamethasone than in patients treated with dexamethasone alone.

Deep Vein Thrombosis and Pulmonary Embolism: Venous thromboembolic events (predominantly deep venous thrombosis and pulmonary embolism) have occurred in patients with MM treated with lenalidomide combination therapy. A significantly increased risk of DVT and PE was observed in patients with MM who were treated with REVLIMID and dexamethasone therapy in a clinical trial.

Allergic Reactions: Angioedema and serious dermatologic reactions including Stevens-Johnson syndrome (SJS) and toxic epidermal necrolysis (TEN) have been reported. These events can be fatal. Patients with a prior history of Grade 4 rash associated with thalidomide treatment should not receive REVLIMID. REVLIMID interruption or discontinuation should be considered for Grade 2-3 skin rash. REVLIMID must be discontinued for angioedema, Grade 4 rash, exfoliative or bullous rash, or if SJS or TEN is suspected and should not be resumed following discontinuation for these reactions.

Tumor Lysis Syndrome: Fatal instances of tumor lysis syndrome have been reported during treatment with lenalidomide. The patients at risk of tumor lysis syndrome are those with high tumor burden prior to treatment. These patients should be monitored closely and appropriate precautions taken.

Most common adverse reactions (≥20%): Fatigue, neutropenia, constipation, diarrhea, muscle cramp, anemia, pyrexia, peripheral edema, nausea, back pain, upper respiratory tract infection, dyspnea, dizziness, thrombocytopenia, tremor and rash

13.2.3 Formulation and Preparation

Lenalidomide will be supplied as capsules for oral administration. Celgene Inc. will provide lenalidomide 5, 10, 15 and 25 mg capsules for the Induction Phase of the protocol and for the extended dosing phase(s).

13.2.4 Stability and Storage

Lenalidomide should be stored at room temperature away from direct sunlight and protected from excessive heat and cold.

13.2.5 Administration Procedures

Celgene Corporation will supply Revlimid® (lenalidomide) to the Clinical Center Pharmacy to be dispensed to study participants at no charge through the REMS® program. Lenalidomide will be shipped directly to patients or picked up directly from the Clinical Center pharmacy. Bottles will contain a sufficient number of capsules for one cycle of dosing; no more than a one-month supply of lenalidomide may be dispensed at one time.

13.2.6 Incompatibilities

Results from human in vitro metabolism studies and nonclinical studies show that REVLIMID is

neither metabolized by nor inhibits or induces the cytochrome P450 pathway suggesting that lenalidomide is not likely to cause or be subject to P450-based metabolic drug interactions in man.

Digoxin: When digoxin was co-administered with lenalidomide, the digoxin AUC was not significantly different; however, the digoxin Cmax was increased by 14%. Periodic monitoring of digoxin plasma levels, in accordance with clinical judgment and based on standard clinical practice in patients receiving this medication, is recommended during administration of lenalidomide.

Warfarin: Co-administration of multiple doses of 10 mg of lenalidomide had no effect on the single dose pharmacokinetics of R- and S-warfarin. Co-administration of single 25-mg dose warfarin had no effect on the pharmacokinetics of total lenalidomide. Expected changes in laboratory assessments of PT and INR were observed after warfarin administration, but these changes were not affected by concomitant lenalidomide administration.

Concomitant Therapies That May Increase the Risk of Thrombosis: Erythropoietic agents, or other agents that may increase the risk of thrombosis, such as estrogen containing therapies, should be used with caution in MM patients receiving lenalidomide with dexamethasone

13.3 DEXAMETHASONE

13.3.1 Source

Dexamethasone will be provided from commercial sources by the NIH Clinical Center Pharmacy Department.

13.3.2 Toxicity

Common:

- Cardiovascular: Hypertension
- Dermatologic: Atrophic condition of skin, Finding of skin healing, Impaired
- Endocrine metabolic: Cushing's syndrome, Decreased body growth
- Gastrointestinal: Disorders of gastrointestinal tract
- Immunologic: At risk for infection
- Musculoskeletal: Osteoporosis
- Ophthalmic: Cataract (5%), Raised intraocular pressure (25%)
- Psychiatric: Depression, Euphoria
- Respiratory: Pulmonary tuberculosis

Serious:

- Endocrine metabolic: Hyperglycemia, Primary adrenocortical insufficiency
- Ophthalmic: Conjunctival hemorrhage (22%), Glaucoma, Vitreous detachment (2%)

13.3.3 Formulation and Preparation

- Oral Tablet (Scored): 4 mg
- Injection, solution, as sodium phosphate: 4 mg/mL (1 mL, 5 mL, 30 mL)

13.3.4 Administration Procedures

- Oral: Administer with meals to decrease GI upset.
- I.V.: Administer intravenously over 10 minutes.

13.3.5 Incompatibilities

- Contraindicated: Praziquantel (theoretical), Rotavirus Vaccine, Live (established)
- Major: Aldesleukin (theoretical), Bupropion (theoretical), Darunavir (theoretical), Dasatinib (theoretical), Etravirine (theoretical), Fosamprenavir (theoretical), Imatinib (theoretical), Ixabepilone (theoretical), Lapatinib (theoretical), Nilotinib (theoretical), Quetiapine (probable), Romidepsin (theoretical), Sunitinib (theoretical), Temsirolimus (theoretical), Thalidomide (probable)

15 APPENDICES

15.1 APPENDIX A: REQUIREMENTS FOR REMS®

Risks of Fetal Exposure, Pregnancy Testing Guidelines and Acceptable Birth Control Methods

Requirements for REMS®

- Patients should be instructed never to give lenalidomide to another person.
- Patients will be asked to take part in a mandatory confidential survey prior to initiation of lenalidomide. To take the survey, they will be instructed to call the Celgene Customer Care Center at [name]. Male patients will be asked to take the survey monthly. Female patients will be asked to take survey periodically (monthly if females of childbearing potential and every 6 months if females of not childbearing potential).
- Female patients should not donate blood during therapy and for at least 28 days following discontinuation of lenalidomide.
- Male patients should not donate blood, semen or sperm during therapy or for at least 28 days following discontinuation of lenalidomide.
- Only enough lenalidomide for one cycle of therapy may be prescribed with each cycle of therapy. Monthly phone counseling is required per the REMS® program in order to prescribe a one-month supply of lenalidomide.
- All patients will be required to sign the REVLIMID, Patient-Physician Agreement Form.
- Males must practice complete abstinence or use a condom during sexual contact with pregnant females or females of childbearing potential throughout the entire duration of lenalidomide treatment, during dose interruptions and for at least 28 days following lenalidomide discontinuation, even if he has undergone a successful vasectomy. See below for further details
- Females of childbearing potential must agree to use two reliable forms of contraception simultaneously or to practice complete abstinence from heterosexual intercourse during the following time periods related to this study: 1) for at least 28 days before starting lenalidomide; 2) throughout the entire duration of lenalidomide treatment; 3) during dose interruptions; and 4) for at least 28 days after lenalidomide discontinuation. See below for further details.

Females not of childbearing potential must sign the REVLIMID, Patient-Physician Agreement Form that says you are presently not pregnant and do not have the ability to have children.

Risks Associated with Pregnancy

The use of lenalidomide in pregnant females and nursing mothers has not been studied nor has the effect of the lenalidomide on human eggs and sperm. Lenalidomide is structurally related to thalidomide. Thalidomide is a known human teratogenic active substance that causes severe life-threatening birth defects. An embryofetal development study in animals indicates that lenalidomide produced malformations in the offspring of female monkeys who received the drug during pregnancy. The teratogenic effect of lenalidomide in humans cannot be ruled out. Therefore, a risk minimization plan to prevent pregnancy must be observed.

All study participants must be registered into the mandatory REMS® program, and be willing and able to comply with the requirements of REMS®.

Criteria for females of childbearing potential (FCBP)

This protocol defines a female of childbearing potential as a sexually mature female who: 1) has not undergone a hysterectomy or bilateral oophorectomy or 2) has not been naturally postmenopausal for at least 24 consecutive months (i.e., has had menses at any time in the preceding 24 consecutive months).

The investigator must ensure that:

- Females of childbearing potential comply with the conditions for pregnancy risk minimization, including confirmation that she has an adequate level of understanding
- Females NOT of childbearing potential acknowledge that she understands the hazards and necessary precautions associated with the use of lenalidomide
- Male patients taking lenalidomide acknowledge that he understands that traces of lenalidomide have been found in semen, that he understands the potential teratogenic risk if engaged in sexual activity with a female of childbearing potential, and that he understands the need for the use of a condom even if he has had a vasectomy, if engaged in sexual activity with a female of childbearing potential.

Contraception

Females of childbearing potential (FCBP) enrolled in this protocol must agree to use two reliable forms of contraception simultaneously or to practice complete abstinence from heterosexual intercourse during the following time periods related to this study: 1) for at least 28 days before starting lenalidomide; 2) throughout the entire duration of lenalidomide treatment; 3) during dose interruptions; and 4) for at least 28 days after lenalidomide discontinuation.

The two methods of reliable contraception must include one highly effective method and one additional effective (barrier) method. FCBP must be referred to a qualified provider of contraceptive methods if needed. The following are examples of highly effective and additional effective methods of contraception:

- Highly effective methods:
 - Intrauterine device (IUD)
 - Hormonal (birth control pills, injections, implants)
 - Tubal ligation
 - Partner's vasectomy
- Additional effective methods:
 - Male condom
 - Diaphragm
 - Cervical Cap

Because of the increased risk of venous thromboembolism in patients with multiple myeloma taking lenalidomide and dexamethasone, combined oral contraceptive pills are not recommended. If a patient is currently using combined oral contraception the patient should switch to one of the effective method listed above. The risk of venous thromboembolism continues for 4–6 weeks after discontinuing combined oral contraception. The efficacy of contraceptive steroids may be reduced during co-treatment with dexamethasone.

Implants and levonorgestrel-releasing intrauterine systems are associated with an increased risk of infection at the time of insertion and irregular vaginal bleeding. Prophylactic antibiotics should be

considered particularly in patients with neutropenia.

Pregnancy testing

Medically supervised pregnancy tests with a minimum sensitivity of 50 mIU/mL must be performed for females of childbearing potential, including females of childbearing potential who commit to complete abstinence, as outlined below.

Before starting lenalidomide

Female Patients:

FCBP must have two negative pregnancy tests (sensitivity of at least 50 mIU/mL) prior to prescribing lenalidomide. The first pregnancy test must be performed within 10-14 days prior to prescribing lenalidomide and the second pregnancy test must be performed within 24 hours prior to prescribing lenalidomide. The patient may not receive lenalidomide until the Investigator has verified that the results of these pregnancy tests are negative.

Male Patients:

Must agree to practice complete abstinence or agree to use a condom during sexual contact with pregnant females or females of childbearing potential throughout the entire duration of lenalidomide treatment, during dose interruptions and for at least 28 days following lenalidomide discontinuation, even if he has undergone a successful vasectomy.

During study participation and for 28 days following lenalidomide discontinuation

Female Patients:

- FCBP with regular or no menstrual cycles must agree to have pregnancy tests weekly for the first 28 days of lenalidomide treatment, including dose interruptions and then every 28 days throughout the remaining duration of lenalidomide treatment, including dose interruptions, at lenalidomide discontinuation, and at Day 28 following lenalidomide discontinuation. If menstrual cycles are irregular, the pregnancy testing must occur weekly for the first 28 days of lenalidomide treatment, including dose interruptions, and then every 14 days throughout the remaining duration of lenalidomide treatment, including dose interruptions, at lenalidomide discontinuation, and at Day 14 and Day 28 following lenalidomide discontinuation.
- At each visit, the Investigator must confirm with the FCBP that she is continuing to use two reliable methods of birth control at each visit during the time that birth control is required.
- If pregnancy or a positive pregnancy test does occur in a study patient, lenalidomide must be immediately discontinued.
- Pregnancy testing and counseling must be performed if a patient misses her period or if her pregnancy test or her menstrual bleeding is abnormal. Lenalidomide treatment must be temporarily discontinued during this evaluation.
- Females must agree to abstain from breastfeeding during study participation and for at least 28 days after lenalidomide discontinuation.

Male Patients:

- Must practice complete abstinence or use a condom during sexual contact with pregnant females or females of childbearing potential throughout the entire duration of lenalidomide

treatment, during dose interruptions and for at least 28 days following lenalidomide discontinuation, even if he has undergone a successful vasectomy.

- If pregnancy or a positive pregnancy test does occur in the partner of a male study patient during study participation, the investigator must be notified immediately.

15.2 APPENDIX B: BONE MARROW ASPIRATE COLLECTION, SORTING AND STORAGE

NOTE: Refer to Section **5.1** for correlative study bone marrow timepoints and study calendar Section **3.4**

Collection of Bone Marrow:

- Orders for bone marrow biopsies should be placed in the Clinical Research Information System (Clinical Research Center, NIH, Bethesda, MD).
- Notify the CCR Hematology lab that flow immunophenotyping is being performed [contact]). The hematology BM collection tech will bring a 10 mL tube sodium heparin Vacutainer tube to the specimen collection site and prepare an extra smear for the Flow Cytometry Laboratory.
- Get sterile heparin suitable for injection from the nurse's station. Rinse syringe and needle with sterile heparin, leaving no less than 0.5 mL in syringe.
- Bone marrow samples will be collected as bone marrow core biopsies and aspirates for analyses. Aspirate first 2 cc of marrow for morphology first and give specimen to Hematology lab technician to be given to Hematology Section, Department of Lab Medicine (1 mL will go to Hematopathology and 1 mL (optionally) will be delivered to [name] for research assessing proteasomes). Reposition needle and, for cellular specimens, slowly aspirate 5-8 mL of bone marrow for flow cytometry and cell sorting.
- Bone marrow core biopsies and one fraction of marrow aspirates will be fixed and paraffin-embedded for histological/immunohistochemical analysis and long term storage. One fraction of marrow aspirates will be stored as air-dried aspirate smears and the rest will be frozen.
- After processing in the pathology department, clot sections will be sent to the Molecular Diagnostics Core Laboratory, LP, NCI under the direction of [name] for determination immunoglobulin heavy and/or light chain rearrangement, and KRAS/NRAS mutations.
- For aspirate specified for flow cytometry under the direction of [name], immediately discharge 1 mL of aspirated marrow syringe into a 10mL sodium heparin Vacutainer, cap tube tightly and mix by gentle inversion 5-6 times. Label tube with patient name, unique identifier number and date. Deliver immediately to the Flow Cytometry Laboratory B1B58 (specimens containing hematopoietic neoplasms have a tendency to clot and must be processed immediately). Call for STAT Escort pickup and delivery if you cannot deliver the specimen yourself [contact]). Aspirate from marrows at baseline, end of cycle 8/or CR reached between cycles 1-8, end of cycle 20/or CR reached between cycles 9-20 and during treatment termination/or CR reached between cycles 21 and beyond will be sent for plasma cell flow cytometry immunophenotyping at [name]'s lab.
- For aspirate specified for flow cytometry under the direction of [name], immediately discharge 1 mL of aspirated marrow syringe into heparin syringe tube.
- For aspirate designated for CD138 sorting, VDJ sequencing, exome sequencing, and microenvironment studies, send remaining aspirate sample [name] Laboratory in the Department of Laboratory Medicine Clinical Center (Attn: [name], [name]). Place aspirate sample in EDTA syringe immediately on ice. Transfer within 30 minutes of sampling to the lab for processing. CD138+ plasma cells will be viably frozen and batched to be sent to Adaptive Technologies for VDJ

Abbreviated Title: CRd in Newly Diagnosed MM
Version Date: 03/27/2020

sequencing and to MSKCC for exome sequencing. CD138- fractions will be studied by Dr.'s [name] and [name]. At subsequent time points, CD138+ sorting will not be done if the patient is in remission.

- For aspirate specified for cytogenetics/FISH, aspirate will be sent to [name]. (NOTE: [name] no longer at NIH/NCI, her involvement ended and these studies no longer being done as of Amendment M.)

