1.1.3 Exploratory Objectives

- To assess MRD detection by next generation VDJ sequencing, exome sequencing, and PD-1/PD-L1 expression in the bone marrow compartment
- To evaluate radiographic changes (signal intensity) in bone marrow heterogeneity and focal lesions by Diffusion Weighted MRI (DW-MRI) over time.
- To evaluate radiographic changes (FDG avidity) in bone marrow heterogeneity and focal infiltration by PET/CT overtime.

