5.1.1 Bone Marrow and Peripheral Blood

- a. During extension phase lenalidomide, bone marrow biopsy and aspirates are optional for those patients that are MRD negative at the end of cycle 8 regardless of response.
- b. Patients may be asked to undergo bone marrow at progression of disease at the discretion of the PI.
- c. Collection of bone marrow, sorting of bone marrow and storage of bone marrow samples is

outlined in **Appendix B** and Section **5.2.1**.

- d. Correlative studies associated with bone marrow specimen will be performed and related to clinical outcome if the results of the study indicate a clinical or translational rationale for analyzing the samples. Such studies may include but are not limited to the following:
- i. Pathology/Immunohistochemistry: Bone marrow biopsy and aspirate will be sent to Clinical Center Department of Laboratory Medicine, Hematology Section for morphological evaluation by [name] and [name], PhD. Immunohistochemical staining will be performed under the direction of [name]. Plasma cell burden will be assessed using immunohistochemistry markers such as CD 138, light chains, CD56 etc. Plasma cells and microenvironment interactions will also be assessed using various immunohistochemistry markers for osteoblasts, osteoclasts, stromal cells and proteasomes.
 - ii. Minimal Residual Disease: Flow cytometry: Immunophenotyping of aberrant plasma cells by flow cytometry currently involves, but is not limited to, the use of the following reagents: CD138, CD19, CD45, CD38, and CD56. Characteristic changes in immunophenotypically abnormal plasma cells (CD138 positive) include but are not limited to absent CD19 and CD45, decreased CD38, and increased CD56. These studies will be performed under the direction of [name] of the flow cytometry unit in the NCI Laboratory of Pathology
 - iii. FISH and cytogenetics: Interphase FISH/cytogenetics will be performed on patients enrolled in this protocol under the direction of [name] of the Molecular Diagnostics Core Laboratory of the NCI Branch. (**NOTE:** [name] no longer at NIH/NCI, her involvement ended and these studies no longer being done as of Amendment M.)

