 - iv. Myelomatous plasma cells will be studied at the single cell level by multiparametric flow cytometry for markers of autophagy, pre- and post-therapy, including but not limited to the technique described by S.T. Rosen *et al. J. Biol. Chem.* 284:26816-26830, 2009 under the direction of [name].
 - v. Flow cytometry for proteasomes under the direction of [name].
 - vi. Cell Sorting, GEP profiling, whole exome sequencing, microRNA analysis and microenvironment interactions - Marrow aspirate will be sent to the lab of [name] ([name]) in the Department of Laboratory Medicine and sorted into CD 138 + and CD 138 – fractions. [name] and [name] will also perform the below assays for unsorted bone marrow aspirate for VDJ sequencing and assessment of MRD negativity.
 - GEP profiling targeted exome sequencing, and VDJ sequencing for MRD assessment: Bone marrow aspirates will be collected and sent to the [name] Lab after 8 cycles of induction or CR, after 20 and 32 cycles of treatment and at annual follow-up milestones where BM aspirates are collected (if the samples were collected from the patients.) At baseline: CD138+ plasma cells will be purified from bone marrow aspirates harvested. Baseline CD138+ cells will be sent for VDJ sequencing and to Memorial Sloan Kettering ([name]) for targeted/whole exome sequencing and molecular expression analyses (depending on resources) in a coded, linked manner. At subsequent time points, once patient is in CR, plasma cells will not be purified and aspirates will be viably frozen. Samples will be sent out in batches. Of note, some samples

- may be sent to FDA/OHOP for next generation sequencing, see below .
- Bone marrow, blood and urine samples, and associated clinical lab data will be sent to Adaptive Biotechnologies Corp. for deep sequencing of the VDJ sequence. Samples and data will be submitted to Adaptive Biotechnologies Corp. in a coded, linked manner.
 - CD 138- fractions will be analyzed for microenvironment interactions such as cytokine profiling, miRNAs, etc. in the [name] Lab. A fraction of CD138- cells will also be cultured to isolate bone marrow stromal cells for further analyses. At the same time points, one 6 ml EDTA tube of peripheral blood will be collected for parallel analysis.
 - Both fractions will be collected, batched, and entered into a biobank. See Section 5.2.1 for storage of bone marrow biobank. As of Amendment N, aspirate samples will be stored in DLM under [name].

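### The documents conflict on whether post-baseline VDJ-sequencing MRD in patients not in CR is measured on sorted CD138+ cells or on unsorted marrow

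*Combined protocol and SAP*

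**What the plan says.** Three places describe how marrow is handled for VDJ sequencing.

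- **Section 5.1.1 (d)(vi).** The laboratory "will also perform the below assays for unsorted bone marrow aspirate for VDJ sequencing and assessment of MRD negativity", with no restriction by response. The same item then says that "Baseline CD138+ cells will be sent for VDJ sequencing and to Memorial Sloan Kettering", and for later samples that "At subsequent time points, once patient is in CR, plasma cells will not be purified and aspirates will be viably frozen".
- **Appendix B (15.2).** The aspirate left after other uses goes to one laboratory for CD138 sorting, VDJ sequencing, exome sequencing and microenvironment work. Of that material, "CD138+ plasma cells will be viably frozen and batched to be sent to Adaptive Technologies for VDJ" sequencing, with no time point given. The exception is that "At subsequent time points, CD138+ sorting will not be done if the patient is in remission".
- **Correlates table in Section 5.1.** The row for CD138+ sorting, expression profiling and microenvironment is marked in the column covering the marrow taken when CR is reached in cycles 2-8, or otherwise at the end of cycle 8.

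Sequencing MRD is an exploratory objective (Section 1.1.3): "To assess MRD detection by next generation VDJ sequencing, exome sequencing, and PD-1/PD-L1 expression in the bone marrow compartment". Section 10.3.2 names only flow cytometry and PET-CT for MRD.

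**The concern.** For a marrow taken after baseline from a patient not in CR, Appendix B as written points to a plasma-cell-enriched fraction, while the opening sentence of 5.1.1 (d)(vi) points to whole aspirate. No sentence says which fraction carries the MRD result. The trigger for stopping sorting also differs: CR in one section and remission in the other. Section 6.3.3.1 has no remission category, so a patient in nCR or VGPR could be handled either way.

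The clonal fraction found by sequencing depends on which cells are sequenced. If the Appendix B rule is followed, the specimen type is set by IMWG response, one of the outcomes that MRD would be related to. Non-CR samples would read higher through handling alone. A patient moving from VGPR or nCR (sorted) to CR (unsorted) would show a fall that is partly artefact, and a patient leaving CR would show a rise of the same kind.

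**Working it through.** The plan states no figure on this point, so there is none to reproduce. The check is a comparison of texts, followed by an illustration on stated assumptions.

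**Step 1. The sections side by side.**

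| Sample | 5.1.1 (d)(vi) | Appendix B | Result |
|---|---|---|---|
| Baseline | sorted CD138+ to VDJ | sorted CD138+ to VDJ | agree |
| Later, in CR | not purified | not sorted, taking remission to include CR | agree |
| Later, not in CR | unsorted by its opening sentence, though purification is implied to continue | sorted CD138+ to VDJ | unresolved |

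The Section 5.1 table adds a third inconsistency. It schedules the sorting row in a column that includes the CR marrow, where both texts say not to sort. That row bundles sorting with profiling and microenvironment studies, so the mark may have been meant for those.

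**Step 2. Do such samples exist?** Yes. Footnote o of the study calendar (Section 3.4) schedules a marrow at the end of cycle 8 if CR has not been reached. Section 5.1.1 (d)(vi) lists aspirates after 8 cycles or CR, after 20 and 32 cycles, and at annual follow-up where collected. Since Amendment L, research marrows are at the discretion of the principal investigator, so the number is not fixed.

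**Step 3. Size of the enrichment.** If the clone lies in the CD138+ fraction and sorting recovers clonal and normal plasma cells alike, then

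E = purity after sorting / plasma-cell fraction before sorting.

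Neither input is in the documents. Assumed values:

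- 20% plasma cells, 80% purity: 0.80/0.20 = 4 (log10 = 0.602)
- 5% plasma cells, 80% purity: 0.80/0.05 = 16 (log10 = 1.204)
- 1% plasma cells, 95% purity: 0.95/0.01 = 95 (log10 = 1.978)

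The 1% to 5% range falls within the marrow limit for CR in Section 6.3.3.1. A patient can miss CR on immunofixation with so low a count, but others will exceed it, hence the 20% case.

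**Step 4. Effect on MRD-negative calls.** Let the true clonal fraction in whole marrow be log-uniform from L to U, with an MRD cut C (all assumed). Then

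P(negative) = [log10(C/E) - log10(L)] / [log10(U) - log10(L)], set to 0 if negative.

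With L = 1e-7, U = 1e-3 and C = 1e-5:

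- unsorted, E = 1: 2/4 = 50%
- E = 4: (2 - 0.602)/4 = 35%
- E = 16: (2 - 1.204)/4 = 20%
- E = 95: (2 - 1.978)/4 = 0.6%

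With L = 1e-5, U = 1e-2 and the same cut, P(negative) is 0% for both sorted and unsorted material. The shift in level (0.6 to 2.0 log10) remains, but the call does not change.

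**The case against.** The strongest reply is that 5.1.1 (d)(vi) already gives the right answer. It assigns unsorted aspirate to VDJ MRD without regard to response, and it sends CD138+ cells for VDJ only in the sentences on baseline. It also says that marrow, blood and urine samples, not sorted cells, go for deep VDJ sequencing. Appendix B refers to Section 5.1 for time points, lists sorting and VDJ sequencing as separate uses of the aspirate, and places its CD138+ sentence before the one on subsequent time points, so that sentence can be read as the baseline step. Sorting part of a sample does not prevent sequencing an unsorted part. This reading is tenable. But Appendix B does not state it, and neither section reserves an unsorted aliquot from a sample that is to be sorted.

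Several stronger claims are tempting and are not supported:

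- A reader might infer that sequencing MRD is in fact measured on enriched cells in patients not in CR. The documents do not say so; it follows only if Appendix B is followed as written.
- A reader might take the words "optional for those patients that are MRD negative at the end of cycle 8 regardless of response" to mean that VDJ MRD is assessed in everyone. They waive extension-phase marrows for certain patients. Footnote o of the calendar explains MRD negative by immunohistochemistry and flow cytometry, not sequencing.
- A reader might infer that handling pushes CR samples toward MRD-negative. They are unsorted in both 5.1.1 and Appendix B, so handling does not shift them.
- A reader might infer that the rule cannot be applied at the marrow that establishes CR, because the sample must reach the laboratory within 30 minutes. That is a transfer limit, not a sorting deadline, and serum and urine results from each induction cycle give advance notice of likely CR.
- The interim result in Section 1.2.10 (5 of 20 below nCR) is best response at a median of 7 cycles. It does not count patients not in CR at the cycle-8 marrow.

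The limited reach also stands. VDJ MRD is exploratory, no pooled analysis of sorted and unsorted samples is specified, and relating marrow studies to outcome is conditional under 5.1.1 (d). Section 13.1.1 refers to active recruitment and treatment in the past tense, so many of the samples at issue appear to have been collected already.

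**Conclusion.** The point holds in a narrow form. The documents conflict on the VDJ MRD input for post-baseline marrows in patients not in CR and use different terms for when sorting stops. At baseline and in CR, 5.1.1 and Appendix B agree.

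If Appendix B is followed, VDJ MRD levels are not comparable across response groups or within a patient entering or leaving CR. On the assumed plasma-cell percentages and purities the shift is 4-fold to 95-fold. Its effect on MRD-negative calls depends on the unknown burden: a 50% rate could fall to between 35% and 0.6% under one assumed distribution, and not change at all under another. These figures illustrate the mechanism and are not estimates for this trial.

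The primary toxicity endpoint, the sample size, and the flow and PET-CT MRD analyses are untouched. This is worth correcting because it could confound an exploratory comparison and the correction is cheap.

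**What to change.** 1. In Appendix B, limit the shipment of CD138+ cells for VDJ sequencing to baseline, where the purpose is to identify the clone.
2. At every later time point, whatever the response, set aside an unsorted aliquot of fixed volume or DNA input before any sorting, and measure VDJ MRD on that aliquot only. The rest may still be sorted for other assays.
3. Align the Section 5.1 table, Section 5.1.1 (d)(vi) and Appendix B on this rule and on one defined trigger term for stopping sorting.
4. Record the input material for every banked sample. Report post-baseline samples that exist only as sorted cells separately, and do not pool them with unsorted samples for MRD level or negativity.

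The cost is a wording change and one pipetting step, with no extra marrow. Slightly fewer cells remain for sorting, and sorted-only banked samples leave the pooled VDJ MRD comparison. As much of the collection appears complete, item 4 may do most of the work; items 1 to 3 apply to any marrows still to be taken.
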